7.2.3. ALT Elevation

An ALT elevation is defined as serum ALT $> 2 \times$ baseline value and $> 10 \times$ ULN, with or without associated symptoms. Confirmed ALT elevation (ALT flare) is defined as ALT elevations at 2 consecutive postbaseline visits. All treatment-emergent ALT elevations including confirmed ALT elevations will be summarized for the randomized phase CCI .

CCI All treatment-emergent and nontreatment-emergent ALT elevations will be included in a listing.

If the first of 2 consecutive results is in the randomized phase and the second is out of the randomized phase (ie, in the CCI TFFU phase), then the result will be considered to be confirmed in the randomized phase (assuming both values meet the criterion). And if the criterion is met by the last value in the randomized phase and no assessments are available after due to the subject exiting the study or data not yet available, then the result will also be considered to be confirmed.

7.2.4. Liver-related Laboratory Evaluations

Liver-related abnormalities after initial study drug dosing will be examined and summarized using the number and percentage of subjects who were reported to have the following laboratory test values for postbaseline measurements:

- Aspartate aminotransferase (AST): (a) > 3 ULN; (b) $> 5 \times$ ULN
- ALT: (a) $> 3 \times$ ULN; (b) $> 5 \times$ ULN
- AST or ALT: (a) $> 3 \times$ ULN; (b) $> 5 \times$ ULN

- Total bilirubin: > 2 x ULN
- AST or ALT > 3 x ULN and total bilirubin > 2 x ULN

For individual laboratory tests, subjects will be counted once based on the most severe postbaseline values. For both the composite endpoint of AST or ALT and total bilirubin, subjects will be counted once when the criteria are met at the same postbaseline visit date. All treatment-emergent liver-related abnormalities will be summarized for the randomized phase CCI. A listing of subjects who met at least 1 of the above criteria will be provided.

7.3. Bone Safety Analysis

The BMD-related analyses for randomized phase summaries will be based on subjects in the Hip or Spine DXA Analysis Set, CCI will be based on subjects in the CCI Spine DXA Analysis Set. Summaries for the entire study treatment period will be based on subjects in the CCI Spine DXA Analysis Set. The analyses of bone biomarkers, fracture events and bone events will be based on subjects in the Safety Analysis Set, CCI will be based on subjects in the CCI.

7.3.1. Bone Mineral Density (BMD)

Observed BMD values will be used for all the analyses described below.

Percentage change from baseline in hip BMD and spine BMD during the entire study treatment period will be summarized by treatment group and visit using descriptive statistics for subjects in the Hip and Spine DXA Analysis Sets, respectively.

For each subject and each visit, the clinical BMD status will be defined for hip and spine BMD based on the corrected t-score in Table 7-1.

Table 7-1. Normal, Osteopenia, and Osteoporosis as Defined by T-score

Clinical Status	BMD T-score
Normal	t-score \geq -1.0
Osteopenia	$-2.5 \leq$ t-score $<$ -1.0
Osteoporosis	t-score $<$ -2.5

The number and percentage of subjects in each clinical BMD status (normal, osteopenia, and osteoporosis) will be summarized by visit and by baseline clinical status for both hip and spine.

The number and percentage of subjects in each category based on percentage change from baseline in hip BMD and spine BMD (> 7% decrease, > 5% to \leq 7% decrease, > 3% to \leq 5% decrease, > 1% to \leq 3% decrease, > 0 to \leq 1% decrease, > 1% to \leq 3% increase, > 1% to \leq 3%

increase, > 3% to ≤ 5% increase, > 5% to ≤ 7% increase, > 7% increase) will be summarized by treatment group and visit.

The above analyses will be repeated in the subgroups based on baseline renal function (eGFR_{CKD-EPI} < 50 ml/min/1.73m² and ≥ 50 ml/min/1.73m²).

Median (Q1, Q3) and mean (95% CI) of percentage change from baseline in observed hip and spine BMD over time will be plotted by treatment group for the entire study treatment period for subjects in the DXA Analysis Set. Listings of hip and spine DXA results will be provided.

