3.7.2. Analysis Visit Windows

Subject visits might not occur on protocol-specified days. Therefore, for the purpose of analysis, observations will be assigned to analysis windows.

The following windows (Table 3-1 to Table 3-5) apply to baseline and on-treatment assessments only. For summaries and analysis, assessments will first be categorized into baseline and on-treatment assessments occurring during the randomized CCI phase, before applying analysis windows.

For subjects who prematurely discontinued the randomized study drug CCI, laboratory assessments up to and including the last dose date of the randomized study drug + 3 days, and DXA assessments up to and including the last dose date of the randomized study drug + 14 days, will be considered as baseline or on-treatment during the randomized phase.

CCI

For subjects who have not discontinued the randomized study drug permanently, data collected up to database finalization date will be considered as baseline or on-treatment of the randomized phase.

CCI

CCI
 CCI

For subjects who discontinue study drug early due to HBsAg loss with confirmed seroconversion, all efficacy data including data collected after the last dose date of the study drug will be reassigned analysis visits using the on-treatment assessment windows (Table 3-1 and Table 3-3).

The analysis windows for HBV DNA, hematology, serum chemistry and liver function tests, eGFR (by CG and CKD-EPI), renal biomarkers urine albumin to creatinine ratio (UACR), urine protein to creatinine ratio (UPCR), renal tubular maximum reabsorption rate of phosphate to the glomerular filtration rate (TmP/GFR), urine fractional excretion of filtered phosphate (FEPO₄), fractional excretion of uric acid (FEUA), non-fasting glucose, weight, and vital sign assessments are provided in Table 3-1.

Table 3-1. Analysis Visit Windows for HBV DNA, Hematology, Serum Chemistry and Liver Function Tests, eGFR (by CG and CKD-EPI), UACR, UPCR, TmP/GFR, FEPO₄, FEUA, Non-fasting Glucose, Weight, and Vital Sign Assessments

Nominal Visit	Nominal Study Day	Lower Limit	Upper Limit
Baseline			1
Week 4	28	2	41
Week 8	56	42	69
Week 12	84	70	111
Week 20	140	112	153
Week 24	168	154	209
Week 36	252	210	293
Week 48	336	294	377 (419 ^b)

[figure not shown]
CCI
 CCI

^b Applies to UACR, UPCR, TmP/GFR, FEPO₄ and FEUA only.

The analysis window for Fasting Glucose, Serum Cystatin C and eGFR by CKD-EPI Cystatin C is in Table 3-2.

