7.2.2.1. Treatment-Emergent Laboratory Abnormalities

Treatment-emergent laboratory abnormalities occurring in the randomized phase are defined as values that increase by at least 1 toxicity grade from baseline at any postbaseline visit up to and including the minimum of the randomized study drug stop date + 3 days **CCI** [REDACTED], for those who discontinued randomized study drug prematurely, or values that increase by at least 1 toxicity grade from baseline at any postbaseline visit for those who are still on the randomized study drug. If the relevant baseline laboratory data are missing, any laboratory abnormality of at least Grade 1 will be considered treatment-emergent.

CCI [REDACTED]

Fasting glucose and nonfasting glucose are graded based on different grading scales. Treatment-emergent laboratory abnormalities will be summarized for fasting glucose and nonfasting glucose separately.

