7.4. Renal Safety Analysis

7.4.1. Confirmed Renal Abnormalities

Confirmed renal abnormalities are defined as follows:

- Confirmed increase from baseline in creatinine of at least 0.5 mg/dL or
- Confirmed increase from baseline in creatinine of at least 0.3 mg/dL or
- Baseline $eGFR_{CKD-EPI} \geq 50$ mL/min/1.73 m² and confirmed postbaseline $eGFR_{CKD-EPI} < 50$ mL/min/1.73 m² or
- Confirmed $eGFR_{CKD-EPI} < 30$ mL/min/1.73 m² or
- Confirmed phosphorous < 2 mg/dL

Treatment-emergent confirmed renal abnormalities will be summarized for randomized phase **CCI**. All confirmed renal abnormalities including those occurred during the 24-week treatment-free follow-up period will be listed.

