7.9. Changes From Protocol-Specified Safety Analyses

Treatment-emergent AE and lab abnormality in randomized phase was defined as any AE or lab abnormality that begins on or after the first dose date of study drug up to the last dose date in the protocol, and is updated in this SAP. Treatment-emergent AE occurring in the randomized phase is defined as any AE with onset date on or after the first dose date of the randomized study and no later than the minimum of the randomized study drug stop date + 3 days CCI [REDACTED], if applicable for the randomized phase. Treatment-emergent laboratory abnormalities occurring in the randomized phase are defined as values that increase by at least 1 toxicity grade from baseline at any postbaseline visit up to and including the minimum of the randomized study drug stop date + 3 days CCI [REDACTED] for the randomized phase. This change was made as labs performed 1-2 days after study drug stopped were being excluded causing the measurement for the timepoint to be missed, even though protocol specified visit windows allowed for labs to be performed in a short period after the study drug was stopped.

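### SAP 7.3.1: the BMD percent-change bands print one increase band twice and have none for 0 to 1% increase

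*SAP*

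**What the plan says.** SAP 7.3.1 asks for the number and percentage of subjects in each band of percent change from baseline in hip and spine BMD, by treatment group and visit. The decrease side has five bands: more than 7%, 5 to 7%, 3 to 5%, 1 to 3%, and 0 to 1%. The list then goes on: "> 0 to \leq 1% decrease, > 1% to \leq 3% increase, > 1% to \leq 3". The increase side ends with 3 to 5%, 5 to 7%, and more than 7%.

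The same section adds: "The above analyses will be repeated in the subgroups based on baseline renal function", with the split at an eGFR of 50. The band table is therefore also produced within each renal subgroup.

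Separately from the bands, SAP 7.3.1 summarizes percent change in BMD as a continuous variable, plots its median and mean over time, and lists the DXA results. Percent change in hip and spine BMD at Weeks 24 and 48 is a secondary safety endpoint (Protocol 3.1.2).

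**The concern.** A set of bands for a table of counts and percentages should place every observed value in exactly one row. This list does not. Small gains and exact zeros have no row, and gains above 1% up to 3% have two rows with the same label.

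A programmer who follows the text must either leave subjects out of the table or choose a band that the plan does not name. The omitted range lies next to zero, where results are likely to be common, and not in a thin tail. What is at stake is the completeness of one descriptive table for a secondary endpoint, and of its subgroup repeats.

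**Working it through.** **Coverage.** Write c for the percent change, negative for a decrease. The printed bands are:

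- Decrease side: c < −7; −7 ≤ c < −5; −5 ≤ c < −3; −3 ≤ c < −1; −1 ≤ c < 0.
- Increase side: 1 < c ≤ 3; 1 < c ≤ 3 (again); 3 < c ≤ 5; 5 < c ≤ 7; c > 7.

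Together they cover c < 0 and c > 1. The range 0 ≤ c ≤ 1 is in no band, and 1 < c ≤ 3 is in two. Testing every value from −10% to +10% in steps of 0.01% gives the same result: 0.00 to 1.00 has no band, and 1.01 to 3.00 has two. If the first duplicate becomes 0 ≤ c ≤ 1, the ten bands cover every value once.

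**Scale.** The documents give no BMD distribution for this trial, so this step is an illustration. Inputs are the Week 48 means and SDs in Protocol Table 1-9 (two Phase 3 studies), a normal distribution (assumed), and the planned arm size of about 25. The share in the gap is Φ((1 − mean)/SD) − Φ((0 − mean)/SD).

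| Site, arm | Mean (SD), % | z limits | Share in gap | × 25 |
|---|---|---|---|---|
| Hip, TAF | −0.163 (2.2437) | 0.073 to 0.518 | 16.9% | 4.2 |
| Hip, TDF | −1.860 (2.4525) | 0.758 to 1.166 | 10.2% | 2.6 |
| Spine, TAF | −0.570 (2.9147) | 0.196 to 0.539 | 12.7% | 3.2 |
| Spine, TDF | −2.366 (3.2051) | 0.738 to 1.050 | 8.3% | 2.1 |

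**Check of the normal assumption.** Table 1-9 also gives observed shares with no decrease and with more than 3% increase. Their difference is the observed share from 0 to +3%: hip TAF 47.5 − 6.8 = 40.7%; hip TDF 20.5 − 2.0 = 18.5%; spine TAF 40.7 − 10.9 = 29.8%; spine TDF 21.9 − 2.7 = 19.2%. The normal model, adding its share from 1 to 3%, gives 16.9 + 22.3 = 39.2%, 10.2 + 9.8 = 20.0%, 12.7 + 18.5 = 31.2% and 8.3 + 10.0 = 18.3%. These are close enough for a statement of scale.

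**Effect on the column totals, in the same order.** With the duplicate shown once, the bands sum to 100% minus the gap: 83.1%, 89.8%, 87.3% and 91.7%. With both copies filled, they sum to 105.4%, 99.6%, 105.7% and 101.6%. A total near 100% in the second case would be coincidence.

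**The case against.** The best reply is that this is a copying slip that any programmer would notice. There are five entries in each direction, and the duplicate sits where the 0 to 1% increase band belongs. The text also breaks inside the second copy, so an extraction fault is possible. Much of this stands: the intended band is easy to guess, and the source file should be checked first. But the break does not explain the gap. The first copy is complete before the break, and removing the second as an artefact would still leave nothing for 0 to 1% increase. The placement of exactly zero also cannot be inferred from the decrease side, which starts strictly above zero.

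A second reply is that the 8% to 17% is borrowed from another population and visit. That also stands. Subjects here are liver transplant recipients already maintained on TDF, and Week 24 is tabulated as well as Week 48.

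A reader might infer that the gap damages the BMD endpoint, or tilts the comparison because the illustrative gap is larger for TAF. The documents do not support this. The endpoint is summarized as a continuous percent change, the band table carries no test, and the distribution in this trial is unknown.

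A reader might also look for a like fault in the renal list in SAP 7.4.1, where "Confirmed $eGFR_{CKD-EPI} < 30$ mL/min/1.73 m² or" has no baseline condition although the summary is called treatment-emergent. The documents do not show an error there. Protocol 7.5.5 uses the same limit regardless of baseline as a retest trigger. SAP 7.4.1 sets the randomized-phase summary against a listing that extends into follow-up ("All confirmed renal abnormalities including those occurred during the 24-week treatment-free follow-up period will be listed"), which points to timing. SAP 7.2.4 likewise calls absolute liver-test limits treatment-emergent without a baseline condition. The CKD stage shift table in SAP 7.4.3 already separates subjects who entered below 30.

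**Conclusion.** The band list in SAP 7.3.1 is wrong as written, with low impact. Changes from exactly 0 to +1% fall in no row, so the table and its two renal-subgroup repeats fail to add to 100% as soon as one subject has such a change. This follows from the printed list alone and needs no distributional assumption, subject only to the check of the source file.

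The size, about 2 to 4 subjects per arm of 25 for each site, rests on Phase 3 means and SDs, normality and the planned arm size, and serves for scale only. The continuous BMD summaries, plots, listings and both primary endpoints do not change.

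**What to change.** Check the source file of SAP 7.3.1. If the list stands as extracted, replace the first of the two identical bands with one for a change of at least 0 and at most 1% increase, and state that exactly zero belongs there. Protocol Table 1-9 gives a precedent, since it groups zero with no decrease. Apply the same bands to hip and spine, at every visit, and in both renal-function subgroups.

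The SAP is signed, so the correction belongs in the clinical study report, as SAP section 1 provides for changes after finalization.

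The cost is one line of text and a rerun of one table with its subgroup repeats, with no new data. The downside is comparability. The Week 24 and Week 48 analyses have been done, and the Week 24 analyses (except PK) are to be reproduced, so the corrected table may differ from any earlier version. A short note in the report should say why.

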7.3.2. Bone Biomarkers

Bone biomarkers include serum CTX, P1NP, PTH, OC, and bsAP.

Baseline, postbaseline, change from baseline, and percentage change from baseline in bone biomarkers will be summarized by treatment group and visit using descriptive statistics during the entire study period.

Median (Q1, Q3) percentage change from baseline in bone biomarkers over time will be plotted by treatment group for the entire study treatment period for subjects in the Safety Analysis Set. A listing of bone biomarker data will be provided.

7.3.3. Fracture Events

The PTs for fracture events were defined based on HLGT of Fractures from current version of MedDRA. Treatment-emergent fracture events will be summarized based on the identified PTs from the HLGT. The number and percentage of subjects who experienced fracture events will be summarized by treatment group for the randomized phase **CCI**. A data listing of fracture events will be provided.

7.3.4. Assessment of Fracture Probability

Fracture probabilities will be assessed using FRAX[®], a computer based algorithm developed by the World Health Organization (WHO; <http://www.shef.ac.uk/FRAX>).

The FRAX algorithm is based on individual patient models that integrate the risks associated with clinical risk factors as well as BMD at the femoral neck. The algorithm provides both the 10-year probability of hip fracture and the 10-year probability of a major osteoporotic fracture (clinical spine, forearm, hip, or shoulder fracture).

The FRAX model is constructed from real data in population-based cohorts around the world that have a limited age range. For an age below 40 or above 90 years, the tool will calculate the probability of fracture at the age of 40 or 90 years, respectively. Due to the age limitation, 2 sets of analyses of fracture probabilities will be performed.

In the first set of analysis, summaries of baseline and change from baseline in the 10-year probabilities of hip fracture, as well as major osteoporotic fracture will be presented by treatment group and visit for subjects aged between 40 and 90 years for the randomized phase.

In the second set of analysis, the above-specified analysis will be performed to include all subjects, where subjects with an age below 40 or above 90 years will be treated as having an age of 40 or 90 years, respectively, in computing their fracture probabilities.

Data listings of fracture risk assessment questionnaire and FRAX fracture probabilities will be provided.

7.3.5. Bone Events

The PTs for bone events were defined based on the Medical Search Term (MST) of Bone Disorders on current version of MedDRA. The number and percentage of subjects who experienced treatment-emergent bone events will be summarized by treatment group for the randomized phase **CCI**. A data listing of bone events will be provided.

7.4. Renal Safety Analysis

7.4.1. Confirmed Renal Abnormalities

Confirmed renal abnormalities are defined as follows:

- Confirmed increase from baseline in creatinine of at least 0.5 mg/dL or
- Confirmed increase from baseline in creatinine of at least 0.3 mg/dL or
- Baseline $eGFR_{CKD-EPI} \geq 50$ mL/min/1.73 m² and confirmed postbaseline $eGFR_{CKD-EPI} < 50$ mL/min/1.73 m² or
- Confirmed $eGFR_{CKD-EPI} < 30$ mL/min/1.73 m² or
- Confirmed phosphorous < 2 mg/dL

Treatment-emergent confirmed renal abnormalities will be summarized for randomized phase **CCI**. All confirmed renal abnormalities including those occurred during the 24-week treatment-free follow-up period will be listed.

7.4.2. Serum Creatinine and Serum Cystatin C

The baseline and change from baseline in serum creatinine and serum cystatin C will be summarized using descriptive statistics for the entire study period.

Median (Q1, Q3) and mean (95% CI) of change from baseline in observed serum creatinine over time will be plotted by treatment group for the entire study period for subjects in the Safety Analysis Set.

A positive shift in serum creatinine values was observed due to a lot calibration change on 01 July, 2018, occurring across Covance laboratory sites worldwide. A correction was therefore applied to records on or after 01 July, 2018 to serum creatinine, following the regression equation specified in Table 7-2. The corrected serum creatinine values will be used for the analyses of serum creatinine, serum creatinine toxicity, eGFR estimated by the Cockcroft Gault formula, eGFR by the CKD-EPI method and other relevant parameters.

The corrected values must be in the same unit as the original values after going through the regression formula in Table 7-2.

- If the unit of serum creatinine is “μmol/L”, then use the formula directly.
- If the unit of serum creatinine is “mg/dL”, the values should be converted to “μmol/L” before using the formula.

After the correction, unit of serum creatinine should be converted back to “mg/dL” for summary and comparison purpose.

Table 7-2. Method of Serum Creatinine Correction

Regional Lab Center	Accession Number ^a	Regular Regression for Serum Creatinine (μmol/L) ^{b, c}
Indianapolis	starts with 65	Y=1.002×X+1.77
Geneva	starts with 62 or 63	Y=1.025×X+2.62
Shanghai	starts with 67	Y=0.971×X+5.42
Singapore	starts with 64 or 66	Y=1.009×X-1.42
Japan	start with 68	Y=1.033×X+7.25

- a Accession numbers specified which regional lab center tested the sample. For example, samples with accession number starting with 65 were tested in Indianapolis Auto Chemistry Center.
- b X and Y are the serum creatinine values from previous lot before 01 July, 2018 and serum creatinine values from new lot on or after 01 July, 2018, respectively.
- c The serum creatinine correction is based on the unit of umol/L. The unit should be converted to mg/dL for summary purposes.

7.4.3. Estimated Glomerular Filtration Rate

The following formulae will be used to calculate eGFR:

- CG:

$$eGFR_{CG} \text{ (mL/min)} = [(140 - \text{age (yrs)}) \times \text{weight (kg)} \times (0.85 \text{ if female})] / (\text{SCr (mg/dL)} \times 72),$$

where weight is actual total body mass in kilograms, and SCr is serum creatinine.

- CKD-EPI Creatinine Based:

$$\text{eGFR}_{\text{CKD-EPI, creatinine}} (\text{mL}/\text{min}/1.73 \text{ m}^2) = 141 \times \min(\text{SCr}/\kappa, 1)^\alpha \times \max(\text{SCr}/\kappa, 1)^{-1.209} \times 0.993^{\text{Age}} \times 1.018 (\text{if female}) \times 1.159 (\text{if black}),$$

where κ is 0.7 for females and 0.9 for males, α is -0.329 for females and -0.411 for males, \min indicates the minimum of SCr/κ or 1, and \max indicates the maximum of SCr/κ or 1 {Levey 2009}.

- CKD-EPI Cystatin C based:

$$\text{eGFR}_{\text{CKD-EPI, cysC}} (\text{mL}/\text{min}/1.73 \text{ m}^2) = 133 \times \min(\text{SCys}/0.8, 1)^{-0.499} \times \max(\text{SCys}/0.8, 1)^{-1.328} \times 0.996^{\text{age}} [\times 0.932 \text{ if female}],$$

where SCys is serum cystatin C.

Change from baseline in eGFR_{CG} , $\text{eGFR}_{\text{CKD-EPI, creatinine}}$ and $\text{eGFR}_{\text{CKD-EPI, cysC}}$ at each postbaseline visit will be provided during the entire study treatment period.

The number and proportion of subjects with decrease from baseline of $\geq 25\%$ and $\geq 50\%$ in eGFR_{CG} , $\text{eGFR}_{\text{CKD-EPI, creatinine}}$ and $\text{eGFR}_{\text{CKD-EPI, cysC}}$ will be summarized by treatment groups for the randomized CCI . CCI

The number and proportion of subjects in each stage of chronic kidney disease (CKD) will be summarized by baseline stages of CKD at each postbaseline visit for the entire study treatment period based on subjects in the Safety Analysis.

The stages of CKD by estimated GFR by CG, CKD-EPI creatinine, CKD-EPI Cystatin C are defined in Section 5.2.

Median (Q1, Q3) change from baseline in eGFR_{CG} , $\text{eGFR}_{\text{CKD-EPI, creatinine}}$ and $\text{eGFR}_{\text{CKD-EPI, cysC}}$ over time will be plotted for the entire study treatment period for subjects in the Safety Analysis Set.

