## 2. OBJECTIVES

The primary objectives of this study are:

- To evaluate the safety and tolerability of TAF 25 mg QD versus TDF-containing regimens as determined by the change from baseline in eGFRCKD-EPI at Week 24
- To evaluate the efficacy of TAF 25 mg QD versus TDF-containing regimens in maintaining viral suppression at Week 24

The secondary objectives of this study are:

- To evaluate the safety of TAF 25 mg QD versus TDF-containing regimens as determined by the percent change from baseline in hip and spine bone mineral density (BMD) at Weeks 24 and 48
- To evaluate the safety of TAF 25 mg QD versus TDF-containing regimens as determined by the change from baseline in serum creatinine at Weeks 24 and 48
- To evaluate the safety of TAF 25 mg QD versus TDF-containing regimens as determined by the change from baseline in eGFRCKD-EPI at Week 48
- To evaluate the efficacy of TAF 25 mg QD versus TDF-containing regimens in maintaining viral suppression at Week 48

The exploratory objectives of this study are:

- [REDACTED]
- [REDACTED]
- [REDACTED]
- [REDACTED]

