### 3. STUDY DESIGN

#### 3.1. Endpoints

##### 3.1.1. Primary Endpoints

The **primary safety endpoint** is:

- Change from baseline in eGFRCKD-EPI of TAF 25 mg QD versus TDF-containing regimens at Week 24

The **primary efficacy endpoint** is:

- Proportion of subjects with HBV DNA < 20 IU/mL at Week 24

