##### **8.6.1. Primary Safety Analysis**

The change from baseline in  $eGFR_{CKD-EPI}$  at Week 24 will be summarized.

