1.1. Study Objectives

The primary objectives of this study are as follows:

- To evaluate the safety and tolerability of TAF 25 mg once daily (QD) versus TDF-containing regimens as determined by the change from baseline in estimated glomerular filtration rate by Chronic Kidney Disease Epidemiology Collaboration formula ($eGFR_{CKD-EPI}$) at Week 24
- To evaluate the efficacy of TAF 25 mg QD versus TDF-containing regimens in maintaining viral suppression at Week 24

The secondary objectives of this study are as follows:

- To evaluate the safety of TAF 25 mg QD versus TDF-containing regimens as determined by the percent change from baseline in hip and spine bone mineral density (BMD) at Weeks 24 and 48
- To evaluate the safety of TAF 25 mg QD versus TDF-containing regimens as determined by the change from baseline in serum creatinine at Weeks 24 and 48
- To evaluate the safety of TAF 25 mg QD versus TDF-containing regimens as determined by the change from baseline in $eGFR_{CKD-EPI}$ at Week 48
- To evaluate the efficacy of TAF 25 mg QD versus TDF-containing regimens in maintaining viral suppression at Week 48

CCI [REDACTED]

[REDACTED]

[REDACTED]

[REDACTED]

[REDACTED]

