3. GENERAL CONSIDERATIONS FOR DATA ANALYSES

Analysis results will be presented using descriptive statistics. For categorical variables, the number and percentage of subjects in each category will be presented; for continuous variables, the number of subjects (n), mean, standard deviation (SD) or standard error (SE), median, first quartile (Q1), third quartile (Q3), minimum, and maximum will be presented.

By-subject listings will be presented for all subjects in the All Randomized Analysis Set unless otherwise specified, and sorted by subject ID number, visit date, and time (if applicable). Data collected on log forms, such as AEs, will be presented in chronological order within a subject. The treatment group to which subjects were randomized will be used in the listings.

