7.2. Laboratory Evaluations

Laboratory data collected during the study will be analyzed and summarized using both quantitative and qualitative methods. Summaries of laboratory data will be provided for the entire study period based on Safety Analysis. Analysis will be based on values reported in conventional units. No formal statistical testing is planned.

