7.2.1. Summaries of Numeric Laboratory Results

Descriptive statistics (sample size, mean, SD, median, Q1, Q3, minimum, and maximum) will be provided by treatment group for each laboratory test during the entire study period specified in the study protocol as follows:

- Baseline values
- Values at each postbaseline analysis window
- Change from baseline to each postbaseline analysis window
- Percentage change from baseline to each postbaseline analysis window (if specified)

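### The primary safety endpoint is worded as TAF versus TDF, but the supplied protocol and SAP plan only by-arm summaries of eGFR change, with no between-arm estimate or confidence interval

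*SAP*

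**What the plan says.** For eGFR (CKD-EPI) at Week 24, Protocol Section 2 words the first primary objective as a comparison: "To evaluate the safety and tolerability of TAF 25 mg QD versus TDF-containing regimens as determined by the change from baseline in" this measure. SAP Section 1.1 repeats it: "To evaluate the safety and tolerability of TAF 25 mg once daily (QD) versus TDF-containing regimens as determined by the change from baseline". Protocol Section 3.1.1 defines the primary safety endpoint as the change in eGFR "of TAF 25 mg QD versus TDF-containing regimens at Week 24".

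The planned analysis is descriptive throughout:

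- Protocol Section 8.6.1: the change "at Week 24 will be summarized".
- SAP Section 3: "Analysis results will be presented using descriptive statistics".
- SAP Section 7.2, on laboratory data: "No formal statistical testing is planned".
- SAP Section 7.2.1: "Descriptive statistics (sample size, mean, SD, median, Q1, Q3, minimum, and maximum) will be provided by treatment group for each laboratory test".
- SAP Section 7.4.3: change in eGFR by three formulae, CKD-EPI creatinine among them, "at each postbaseline visit will be provided during the entire study treatment period", plus a plot of the median and quartiles over time.

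No redaction interrupts the change-from-baseline sentence in Section 7.4.3 or the text of Protocol Section 8.6.1. SAP Section 7.9, which lists departures from the protocol's safety analyses, does not mention eGFR.

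**The concern.** The endpoint names a comparison and the analysis does not make one. As these two documents stand, the report would show two columns of summary statistics and leave the reader to work out the difference and its precision. A reader could form a valid crude interval from the planned n, mean and SD, but could not recover an estimate adjusted for baseline eGFR and the randomisation stratum from those tables.

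The exploratory label does not explain the gap. Protocol Section 8.5.1 specifies, for the primary efficacy endpoint of the same study, a two-sided 95% interval for TAF − TDF adjusted for the stratification factor. An interval for eGFR needs no hypothesis test, so it is compatible with the absence of a sample size calculation and of formal laboratory testing.

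The gap is limited to the stated comparison. The SAP keeps other useful renal summaries: eGFR decreases of at least 25% and 50%, shifts in CKD stage, and confirmed eGFR below 30.

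**Working it through.** The documents give no SD, effect size, power or precision for eGFR change, so there is no planned figure to reproduce. The calculations below show how precise the missing contrast would be, and what adjustment would add.

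**1. Reference from the Phase 3 data.** Protocol Section 1.2.3 gives median (Q1, Q3) changes in Cockcroft-Gault eGFR at Week 48 of −1.2 (−8.4, 7.5) for TAF and −5.4 (−12.0, 3.0) for TDF. The population, formula and visit all differ from this trial's, so this is a scale only. Assuming normality, SD = IQR/1.349:

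- TAF: (7.5 + 8.4)/1.349 = 11.79
- TDF: (3.0 + 12.0)/1.349 = 11.12

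The standard error of the difference is √[(11.79² + 11.12²)/n].

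- 25 per arm: SE = 3.24; half-width = t(0.975, 48) × 3.24 = 6.5 mL/min.
- 20 per arm: SE = 3.62; half-width = t(0.975, 38) × 3.62 = 7.3 mL/min.

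**2. Crude interval over a range of assumed SDs.** Half-width = t(0.975, 48) × SD × √(2/25):

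- SD 6: 3.41
- SD 8: 4.55
- SD 10: 5.69
- SD 12: 6.82 mL/min/1.73 m²

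**3. Effect of adjustment, by simulation (8,000 trials per setting, N = 50, 1:1).** From the documents come N, the allocation, the stratum cut at 50, and the target of about 40 of 50 subjects with eGFR below 60. Everything else is assumed:

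- Baseline: 40 subjects uniform on 15–60 and 10 uniform on 60–90. The variance is 0.8 × 168.75 + 0.2 × 75 + 0.8 × 0.2 × 37.5² = 375, so the SD is 19.4.
- Screening value: baseline plus N(0, 4) noise.
- Randomisation: permuted blocks of 4 within strata.
- True difference: 4.2, the gap between the two Phase 3 medians.
- Equal SD at baseline and follow-up, which fixes the slope of change on baseline at −(SD of change)²/(2 × 19.4²).

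| SD of change | Slope | Crude half-width | ANCOVA, baseline | ANCOVA, baseline + stratum | Gain over crude | Crude vs adjusted estimate: median (95th percentile) |
|---|---|---|---|---|---|---|
| 6 | −0.048 | 3.40 | 3.37 | 3.40 | 0.00 | 0.13 (0.65) |
| 8 | −0.085 | 4.52 | 4.44 | 4.48 | 0.04 | 0.19 (0.95) |
| 10 | −0.133 | 5.67 | 5.49 | 5.54 | 0.13 | 0.28 (1.34) |
| 12 | −0.191 | 6.80 | 6.48 | 6.53 | 0.27 | 0.38 (1.70) |

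With SD 10 and a steeper slope of −0.2, the follow-up SD falls to √(375 + 100 − 2 × 0.2 × 375) = 18.0. The half-widths are then 5.68 crude and 5.29 with full adjustment, a gain of 0.39. Coverage of both intervals is 0.94 to 0.96 in all settings. Adding the stratum to baseline eGFR widens the interval by 0.03 to 0.05.

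**The case against.** The strongest objection is that this SAP covers the final analysis only. SAP Section 2.1.2 says that the primary Week 24 analysis followed its own SAP of 19 March 2018, and that its analyses other than PK will be reproduced. An eGFR contrast specified there could reach the final report without appearing in Section 7.4.3. Silence here is weak evidence, because this SAP's efficacy sections (6.1.2, 6.2.2) also fail to repeat the adjusted efficacy interval that the protocol requires, and Section 6.3 does not list that omission as a change. This point stands. It limits the conclusion to the supplied documents and makes checking the Week 24 SAP the first step.

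A second objection is that side-by-side summaries are acceptable in an exploratory Phase 2 study, and that the secondary bone and creatinine endpoints use the same comparative wording with only summaries planned. Both statements are true. But the protocol itself went further for its primary efficacy endpoint, and eGFR is the primary safety endpoint.

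Third, adjustment gains little precision, and any model chosen now is post hoc in an open-label trial whose Week 24 and Week 48 analyses are done. Both points stand. The case rests on stating the comparison, with a post hoc label.

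Fourth, subjects with confirmed eGFR below 15 must stop treatment, so on-treatment values may omit some renal failures. That limitation is real, but it affects the planned descriptive tables equally.

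**Conclusion.** The concern holds for the supplied protocol and SAP: a comparative primary safety endpoint has only a by-arm descriptive analysis. Nothing planned is invalid, and no hypothesis test is needed. The unstated uncertainty is several mL/min/1.73 m² in each direction: about 3.4 to 6.8 at 25 per arm for assumed SDs of 6 to 12, against a reference value of 6.5 mL/min from the Phase 3 Cockcroft-Gault quartiles. Adjustment narrows the interval by 0 to 0.3 in the main settings and by 0.4 in the steeper-slope case. Within a trial it typically moves the estimate by 0.1 to 0.4, and by more than 0.7 to 1.7 in one trial in twenty. All of these figures rest on assumed SDs, and the adjusted figures also on the assumed baseline distribution. This is a cheap improvement. Confidence is high for the supplied documents; what the Week 24 SAP specifies is unknown.

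**What to change.** First check the Week 24 SAP. If it specified an eGFR contrast, reproduce that one.

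Otherwise add to SAP Section 7.4.3, for change in eGFR CKD-EPI (creatinine) at Weeks 24 and 48:

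- **Model:** an ANCOVA with treatment, baseline eGFR and randomisation stratum (below 50, or 50 and above, as recorded in IXRS).
- **Report:** the TAF − TDF least-squares mean difference with its 95% confidence interval, as estimation without a test.
- **Data:** the Safety Analysis Set and the on-treatment values already defined in SAP Section 3.7.2.
- **Label:** specified after the Week 24 and Week 48 analyses.

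Keep every planned descriptive table. The cost is one SAP paragraph and one table with two rows, from data already collected, with no new visits or patients. The addition cannot supply pre-commitment, and its precision gain over a crude interval is small.
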